1 PROTOCOL SUMMARY

1.1 SYNOPSIS

Title:	Theta-burst stimulation modulates criticality, working memory and subjective effort
Grant Number:	K99MH125021
Study Description:	In this study we test the hypotheses that critical brain dynamics depend on the balance of cortical excitation to inhibition and that sub-criticality impacts on subjective cognitive effort and capacity for working memory tasks.
Objectives[*]:	Primary Objective: Test whether continuous theta burst stimulation can alter critical dynamics, working memory, and cognitive effort. Secondary Objectives: Test whether the effects of continuous theta burst stimulation reflect alterations in the cortical excitation to inhibition balance.
Endpoints[*]:	Primary Endpoint: Long-range temporal correlations and avalanche branching statistics from EEG signals. Working memory performance. Cognitive effort discounting of rewards. Secondary Endpoints: Functional E/I ratio estimated from EEG data.
Study Population:	We will recruit 30 healthy young adults (15 F and 15 M; all 18-45 years old), from the Brown University Community in Providence, Rhode Island.
Phase[*] or Stage:	N/A
Description of Sites/Facilities Enrolling Participants:	This single-site study will be conducted at Brown University in the Magnetic Research Facility, the Carney Human Testing Space, and the Metcalf Research Building. No research will be conducted overseas.
Description of Study Intervention/Experimental Manipulation:	The study will involve two sessions of within-subject, sham-controlled continuous theta burst stimulation delivered either at the left dorsolateral prefrontal cortex (target) or angular gyrus (sham).
Study Duration[*]:	Nine Months
Participant Duration:	Participants will complete all components within 4 months of their first visit.

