3 OBJECTIVES AND ENDPOINTS

OBJECTIVES	ENDPOINTS	JUSTIFICATION FOR ENDPOINTS	PUTATIVE MECHANISMS OF ACTION
Primary			
Test whether continuous theta-bursts stimulation induces sub-critical dynamics in the cortex	Diminished markers of critical dynamics include reduced long-range temporal correlations measured by detrended fluctuation analysis, and sub-critical avalanche branching ratios.	Long-range temporal correlations and avalanche branching dynamics are widely used metrics of distance from the critical point (degree of sub-criticality) in EEG studies.	Long-range temporal correlations and avalanche branching ratios of 1.0 are emergent properties of dynamical systems at a critical point. By reducing the E/I balance, continuous theta burst stimulation should make the brain more sub-critical, thus dampening these emergent properties.
Test whether continuous theta-bursts stimulation to dlPFC diminishes working memory function relative to stimulation to the angular gyrus.	Lower discrimination (d') accuracy and slower reaction times on the N-back following dlPFC stimulation.	Criticality affords dynamic flexibility as needed for rapid, reliable updating in the N-back task, and also flexible task switching. Prior work has shown that dlPFC continuous theta burst can undermine working memory function. Here we test the specific hypothesis that this reflects the effects	A decrease in the E/I balance in the dlPFC produced by dlPFC theta-burst stimulation should make the brain more sub-critical, thus impairing functional flexibility afforded by a critical state. This should matter most

OBJECTIVES	ENDPOINTS	JUSTIFICATION FOR ENDPOINTS	PUTATIVE MECHANISMS OF ACTION
		of TMS-induced sub-criticality in the dlPFC.	in the dlPFC which is a key nexus of higher-order working memory function.
Test whether continuous theta burst stimulation to the dlPFC increases subjective cognitive effort relative to stimulation to the angular gyrus.	Steeper discounting of rewards contingent on the expenditure of cognitive effort following dlPFC stimulation versus angular gyrus stimulation.	By virtue of dlPFC's involvement in working memory and cognitive control, it is hypothesized to play a key role in subjective cognitive effort. We specifically predict that critical dynamics in the dlPFC are what the brain tracks as subjective effort.	
Secondary			

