Test whether continuous theta-burst stimulation decreases E/I balance	Decrease in the functional E/I (fE/I) balance ratio at rest, estimated from EEG data after TMS	The fE/I measure derived from EEG activity has been shown to index E/I balance in silico, and in vivo with humans taking GABAergic medication. Thus, in principle, a change in E/I balance induced by TMS should also be apparent in the EEG dynamics and thereby the fE/I of channels near the stimulation site. Changes in fE/I should moderate effects of theta-burst stimulation on critical dynamics and	Theta-burst stimulation is thought to promote inhibitory neurotransmission, at diverse timescales, thus decreasing E/I balance in local microcircuits. The fE/I measure should be sensitive to these neuromodulatory changes.
Control for session order effects on task performance, subjective effort.	Effects of session order on accuracy (d') and reaction times in working memory task, on	Session order will be included as a covariate in all analyses since participants improve discrimination accuracy and response	Practice improves performance, and people find tasks with which they have more practice

OBJECTIVES	ENDPOINTS	JUSTIFICATION FOR ENDPOINTS	PUTATIVE MECHANISMS OF ACTION
	discounting of rewards as a function of subjective effort.	speed across sessions with the working memory task. In turn, they find tasks to be less effortful across sessions.	to be subjectively easier.
Tertiary/Exploratory			

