9.1 STATISTICAL HYPOTHESES

- Primary Endpoint(s):

We predict that, relative to pre-stimulation rest, continuous theta burst stimulation (cTBS) will result in a reduction of the local balance of cortical excitation to inhibition as reflected in the functional E/I balance in proximity to stimulated targets.

We also predict that, relative to pre-stimulation rest, cTBS will result in a reduction in markers of critical dynamics (including, e.g., long-range temporal correlations) in proximity to stimulation targets.

Finally, we predict that, relative to angular gyrus stimulation, cTBS to the dorsolateral prefrontal cortex will increase subjective cognitive effort.

- Secondary Endpoint(s):

We hypothesize that subjective effort reflects divergence from a critical state and that criticality depends on the E/I balance. As such, we predict that there will be individual difference correlations in the degree to which TMS perturbs E/I balance, alters measures of criticality including long-range temporal correlations, and ultimately amplifies subjective effort.

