9.4.2 ANALYSIS OF THE PRIMARY ENDPOINT(S)

The following key outcomes will be assessed in this study. All measures are interval with the exception of the categorical covariate of sex.

- Subjective effort
 - Likert scale ratings (ranging from 1-10) of task-induced effort, demand, time pressure, and stress
 - subjective values as estimated from an indifference point discounting procedure
 - self-reported motivation to engage in demanding tasks on a set of Likert scales with continuous values ranging from 0-20
- E/I balance
 - fEI derived measure with exponents ranging approximately from 0.0-2.0
 - power-law exponents with exponents approximating -2.0
- Critical dynamics
 - Long range temporal correlations – a derived measure with exponents ranging approximately from 0.5-1.0
 - Avalanche size and duration distribution exponents approximating -2.0 and -1.5, respectively
- N-back working memory performance
 - overall accuracy rate as a percentage
 - median correct reaction times by trial type: lures versus targets versus regular trials
 - the discrimination index d'

Primary analyses of these outcomes will entail multiple regression models in which outcomes will be regressed on cTBS condition (target versus sham), controlling for sex and age.

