9.4.3 ANALYSIS OF THE SECONDARY ENDPOINT(S)

Secondary endpoints will be inter-correlations among the primary endpoint measures. Namely, these correlations will test whether the degree to which cTBS alters one measure correlates with stimulation effects on other measures. Given the large number of possible correlations, we will only test for correlations among those measures which show a reliable stimulation effect in the first place. We will then correct for multiple comparisons among these correlations by the false discovery rate method to control for Type I errors, limiting them to no more than 5% chance.

We will use Pearson's correlations for all tests since our outcome measures are continuous, interval measures.

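### The primary endpoint set contradicts itself across Sections 1.1, 3, 9.1 and 9.4.2, so the family for the promised multiplicity correction is not fixed

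*Protocol*

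**What the plan says.** **Functional E/I.** The synopsis (Protocol 1.1) states "Secondary Endpoints: Functional E/I ratio estimated from EEG data". Section 3 places under its secondary heading "Decrease in the functional E/I (fE/I) balance ratio at rest, estimated from EEG data after TMS". Section 9.1, under its primary heading, first predicts a "reduction of the local balance of cortical excitation to inhibition as reflected in the functional E/I balance in proximity to stimulated targets". Section 9.4.2, on the primary endpoints, lists an "fEI derived measure with exponents ranging approximately from 0.0-2.0". Section 9.4.3 then says "Secondary endpoints will be inter-correlations among the primary endpoint measures", in line with the secondary hypothesis in 9.1 about "individual difference correlations in the degree to which TMS perturbs E/I balance".

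**Avalanche measures.** Section 3 includes "sub-critical avalanche branching ratios" in the primary endpoint and gives 1.0 as the value at the critical point. Section 9.4.2 lists "Avalanche size and duration distribution exponents" and no branching ratio. Sections 1.1 and 1.3 use the looser label of avalanche branching statistics. Section 9.1 names long-range temporal correlations (LRTC) only as an example of a criticality marker.

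**Working memory.** It is primary in 1.1, 3 and 9.4.2 and is the sole basis of the sample size in 9.2. Section 9.1 does not list it under either heading.

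**Multiplicity.** Section 9.4.1 sets p < 0.05 for all tests and promises correction for multiple comparisons. The only method named is the false discovery rate, in 9.4.3, for the secondary correlations. Section 9 states that there will be no formal SAP. Section 9.2 claims 80% power at d = 0.53 with 30 participants.

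**The concern.** A multiplicity correction needs a fixed list of tests. Here the sections disagree on whether fE/I belongs to that list, whether the avalanche measure is a branching ratio or a pair of exponents, and whether working memory is among the stated hypotheses. Section 9.4.2 also gives several measures per construct. Section 9.4.1 says that multiple measures serve to assess reliability, but no section says which one carries the test.

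The contrast is open too: 9.1 (for fE/I and criticality) and 9.4.1 speak of change from before to after stimulation, while 9.4.2 regresses outcomes on target versus control site.

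At stake is which results count as positive. With the list open, the corrected threshold and the measure that decides success could be settled after the data are seen. The power statement in 9.2 is also affected, because it takes no account of the correction that 9.4.1 promises.

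**Working it through.** **1. Status of each item, by section**

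| Item | 1.1 | 3 | 9.1 | 9.4.2 |
|---|---|---|---|---|
| fE/I | secondary | secondary | primary | primary |
| LRTC | primary | primary | example of a marker | primary |
| Branching ratio | under a looser label | primary | not named | no line |
| Avalanche size and duration exponents | not named | not named | not named | primary |
| Working memory | primary | primary | not listed | primary |
| Subjective effort / discounting | primary | primary | primary | primary |

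The fE/I row conflicts outright. Section 9.4.3 does not resolve it: there the secondary endpoints are only correlations among primary measures, so fE/I enters those correlations as a primary measure. In the branching-ratio row, the clear mismatch is between Section 3 and 9.4.2.

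**2. Reproducing the stated power**

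Inputs from 9.2: n = 30, d = 0.53, alpha 0.05. The test is not stated; I assume a two-sided paired t-test.

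- Degrees of freedom: 30 − 1 = 29.
- Noncentrality: d × √n = 0.53 × √30 = 2.903.
- Critical value: t(0.975; 29) = 2.045.
- Power = P(|T| > 2.045), with T noncentral t = 0.801.

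This reproduces the stated 80%, for one test without correction.

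**3. The same calculation after correction**

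No method is named for the primary tests, so I use Bonferroni, alpha = 0.05/k, as an illustration. The noncentrality stays at 2.903.

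| Primary tests k | Alpha per test | Critical t (29 df) | Power at d = 0.53 | Effect detectable with 80% power |
|---|---|---|---|---|
| 1 | 0.0500 | 2.045 | 80.1% | 0.53 |
| 3 | 0.0167 | 2.541 | 64.2% | 0.62 |
| 4 | 0.0125 | 2.663 | 59.8% | 0.64 |
| 5 | 0.0100 | 2.756 | 56.4% | 0.66 |

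**4. Dependence on the method**

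Simulation with four tests (60,000 trials, n = 30):

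- Only one effect real, at d = 0.53: about 60% power with either Holm or Benjamini-Hochberg.
- All four effects at d = 0.53, correlation between tests from 0.6 to 0: 70–72% with Holm and 75–77% with Benjamini-Hochberg.

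**5. Dependence on the effect size**

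At d = 1.39 the noncentrality is 1.39 × √30 = 7.613, and power stays above 99.9% for k = 3, 4 and 5.

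**The case against.** **The sections are closer than they look.** Counted by domain, 1.1, 3 and 9.1 each have three primary items and only 9.4.2 has four. This stands. A reader might infer that the sections imply families of 3, 4 and 5, each with its own power. That would mix hypotheses, endpoints and measures, and it would apply working-memory power to the 9.1 list, which omits working memory. What the sections do disagree on is membership: fE/I is in or out, and so is working memory.

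**fE/I is not left untested.** A reader might infer from 9.4.3 that it has no analysis. It has one: 9.4.2 regresses it on stimulation condition. The defect is its status and whether it counts in the primary family.

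**The branching label.** The wording in 1.1 and 1.3 can cover size and duration exponents, so the mismatch is with Section 3 alone.

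**Working memory is not an unstated hypothesis.** Sections 3, 4.1 and 6.1.1 state the prediction, 9.4.1 names it among the key t-tests and 9.4.2 lists it. The gap is in the 9.1 list only.

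**The power loss is conditional.** It arises at the fallback effect, under an assumed correction and a paired t-test, whereas 9.4.2 plans regression with sex and age. The multi-effect figures assume d = 0.53 for outcomes to which 9.2 gives no effect size. All of this stands, and the documents do not support calling the trial underpowered at its planning effect.

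**Such detail often sits in a SAP or a registry entry.** Section 9 says that no formal SAP will exist and that no statistical plan will be posted or registered before the start. Section 10.1.11 promises a ClinicalTrials.gov entry, whose content cannot be seen here. That entry might fix the list, but it would not remove the contradiction within the protocol.

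**Conclusion.** The point holds as a conflict of status and membership. fE/I is secondary in two sections and primary in two others; Section 3's branching ratio is missing from 9.4.2; working memory is missing from 9.1; and the promised correction has neither a fixed primary family nor a named method.

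The stated 80% power applies to one uncorrected test. Under Bonferroni with 3 to 5 primary tests it would be about 64% to 56%, and less conservative methods lose less if several effects are real. These figures rest on a two-sided paired t-test with 30 complete participants and an assumed family size and method. They illustrate the size of the issue and are not attached to particular sections. Certainty about the textual conflict is high; its effect on the results depends on how the family is eventually set. It should be corrected.

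**What to change.** - **One primary list** in 1.1, 3, 9.1 and 9.4.2, with one tested measure per endpoint. For example: LRTC (detrended fluctuation exponent), avalanche branching ratio, N-back d' at a stated load (9.2 sizes on the 2-back), and subjective value from discounting. Label the other measures in 9.4.2, including reaction time, supportive or secondary.
- **One contrast per endpoint:** state whether the test compares before with after stimulation, or target with control site.
- **One status for fE/I.** If secondary, edit 9.1, 9.4.2 and 9.4.3 so that it keeps its own test and its place in the planned correlations. If primary, edit 1.1 and 3 and count it in the family.
- **Fill the gaps:** add the branching ratio to 9.4.2 and the working-memory hypothesis to 9.1.
- **Name the correction** across the primary list in 9.4.1, for example Holm.
- **Restate 9.2:** say that 80% at d = 0.53 is for one uncorrected paired test, and give the corrected figure.

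The cost is text alignment, with no new data and no added enrolment. Some measures lose primary status, and the stated power at d = 0.53 falls; for four tests it would be about 60% with Bonferroni, and up to 72% with Holm if all four effects are real at that size.

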4 STUDY DESIGN

4.1 OVERALL DESIGN

The hypothesis to be studied in this Trial is that criticality in the brain depends on the balance of cortical excitation to inhibition and that sub-criticality impacts on working memory and subjective cognitive effort. This hypothesis leads to predictions including that TMS protocols which decrease the cortical excitation to inhibition ratio (like theta burst stimulation) will make the brain more sub-critical. In turn, when theta-burst stimulation is targeted at regions involved in working memory like the dorsolateral prefrontal cortex, this predicts worse, more inflexible working memory performance and greater subjective effort when people are engaged in working memory tasks.

We will use a repeated measures design wherein every subject is their own control. Specifically, on different days, separated by at least one week, participants will receive continuous theta burst stimulation to either their dorsolateral prefrontal cortex (the active condition) or the angular gyrus (the control condition). The order of these sessions is pseudo-randomized across participants. Specifically, 15 of our target 30 participants will be randomly pre-assigned to complete an active condition session first and control condition second and vice versa for the other 15 participants. The pre-assignment will be determined by permutation of a list of subject numbers before recruitment starts. Every subject number will subsequently be assigned to participants in order of their recruitment. Errors in randomization will be documented and session order will be included as a covariate in all analyses.

Participants will come in for three sessions: 1) a first session to complete paperwork and an MRI structural scan for subsequent neuronavigation and a resting state scan, 2) one counterbalanced order session for dorsolateral prefrontal cortex stimulation and working memory task performance and 3) another counterbalanced order session for angular gyrus stimulation and working memory task performance. The first stimulation session can happen the day after an MR scan (but no more than 113 days after the MR

scan) and the second stimulation session can happen one week after the first stimulation session (but no more than 113 days after the first stimulation session).

This is a single-site trial.

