6 STUDY INTERVENTION(S) OR EXPERIMENTAL MANIPULATION(S)

6.1 STUDY INTERVENTION(S) OR EXPERIMENTAL MANIPULATION(S) ADMINISTRATION

6.1.1 STUDY INTERVENTION OR EXPERIMENTAL MANIPULATION DESCRIPTION

The study intervention is modulation of cortical excitation to inhibition (E/I) balance in the dorsolateral prefrontal cortex (dlPFC) by means of 2 trains of spaced continuous theta burst stimulation (cTBS) using a transcranial magnetic stimulation device. As prior work (Huang et al 2005; Chung et al. 2018) has shown that cTBS reliably decreases the cortical E/I ratio with diverse cortical targets, we expect to replicate a reduction in E/I balance when applied to the dlPFC. The mechanism of action is thought to be an increase in inhibitory neurotransmission across diverse timescales. The endpoint of this stimulation will be a decrease in the local E/I ratio that should last at least 60 minutes post-stimulation (Chung et al., 2018).

We will assess the change in E/I balance by quantifying the functional E/I ratio as previously done in a study of the GABA receptor agonist Zolpidem (Bruining et al. 2020). We furthermore anticipate that a reduction in dlPFC E/I balance will also make the dynamics of dlPFC neurons more sub-critical (Pfeffer et al. 2018; Poil et al. 2012), hence we will test the prediction that cTBS weakens long-range temporal correlations otherwise found in the brain in a critical state. Moreover, we will test the prediction that cTBS to the dlPFC will undermine working memory performance and amplify subjective effort, given the role of the dlPFC in working memory processes.

Importantly, we will contrast the effects of dlPFC cTBS with control cTBS to the angular gyrus. Active stimulation of a control region is preferable to sham stimulation since the latter is less convincing than active control stimulation and may present a confound of participant awareness. Also, the angular gyrus is a suitable control region because, unlike the dlPFC, it is not part of the frontoparietal or dorsal attention networks which have been implicated in working memory and cognitive control (Power et al. 2011) and moreover has a low participation coefficient indicating that it is minimally coupled with these networks (Power et al. 2013).

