6.1.2 ADMINISTRATION AND/OR DOSING

As noted, the intervention is spaced, cTBS to either (in alternate sessions) the anatomically-defined dlPFC or angular gyrus. Each session will thus entail two trains of 50 Hz triplet bursts of stimulation delivered at 5 Hz (theta rhythm) continuously for 40 seconds (600 pulses for each train for a total of 1200 pulses) at an intensity based on 80% of a participant's active motor threshold to either the target or control region. These two trains will thus constitute the full-dose intervention in either location.

Each participant will have their own personal set of two sessions and will thus not interact with other participants during the study.

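### The synopsis and the primary model call the angular gyrus condition sham, but it is a full-dose active control, so the 9.4.2 coefficient is a site difference and does not test the Section 9.1 predictions on E/I balance and criticality

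*Protocol*

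**What the plan says.** Two places in the protocol call the comparator sham.

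- Section 1.1 (Synopsis): "two sessions of within-subject, sham-controlled continuous theta burst stimulation delivered either at the left dorsolateral prefrontal cortex (target) or angular gyrus (sham".
- Section 9.4.2 (primary analysis), for every outcome listed there: "outcomes will be regressed on cTBS condition (target versus sham), controlling for sex and age".

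The sections that define the intervention describe an active control.

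- Section 4.1: "participants will receive continuous theta burst stimulation to either their dorsolateral prefrontal cortex (the active condition) or the angular gyrus (the control condition".
- Section 6.1.2 gives the two trains "at an intensity based on 80% of a participant's active motor threshold to either the target or control region" and adds: "These two trains will thus constitute the full-dose intervention in either location".
- Section 6.1.1 gives the reason: "Active stimulation of a control region is preferable to sham stimulation since the latter is less convincing than active control stimulation".

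The hypotheses do not share one reference. Section 9.1 sets the E/I and criticality predictions against rest before stimulation, near the stimulated sites. It sets the effort prediction against angular gyrus stimulation. Section 3 follows the same split for criticality and effort. Its first primary objective, "Test whether continuous theta-bursts stimulation induces sub-critical dynamics in the cortex", names no comparator site, while the working memory and effort objectives are both worded against the angular gyrus.

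Section 9.4.1 says the regression is meant to ask if cTBS changes the outcomes. It also plans pre-post t-tests for E/I, working memory and criticality.

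**The concern.** Sham ordinarily means that the comparator receives no effective stimulation. Under that label a reader takes the 9.4.2 coefficient as the effect of cTBS, and the stated purpose of the regression in 9.4.1 encourages this. A null would then read as evidence that cTBS does not alter E/I balance or criticality.

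The comparator is in fact stimulated under the same dosing rule, so the coefficient answers a different question: does cTBS at dlPFC differ from cTBS at the angular gyrus? That is the right question for working memory and effort. For E/I and criticality it is not the question posed in 9.1, yet 9.4.2 makes it the primary analysis for those outcomes too.

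**Working it through.** **1. Dose at each site (Sections 4.1 and 6.1.2).** Each train is triplet bursts at 5 Hz for 40 seconds.

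- Pulses per train: 40 × 5 × 3 = 600, as stated.
- Pulses per session: 2 × 600 = 1200, as stated.
- Intensity rule: based on 80% of active motor threshold, at target or control.

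The two sessions differ in site, not in dose. No session is unstimulated.

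**2. What the 9.4.2 coefficient estimates.** Let D be the change that cTBS at dlPFC produces in a measure, and A the change that cTBS at the angular gyrus produces in the measure entered for that session. A true sham comparator would give D. This comparator gives D − A.

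**3. Match between hypothesis and analysis.**

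| Outcome | Reference in 9.1 or Section 3 | 9.4.2 primary contrast | Match |
|---|---|---|---|
| Working memory | Angular gyrus stimulation (Section 3) | dlPFC minus angular gyrus | Yes |
| Subjective effort | Angular gyrus stimulation (Section 3 and 9.1) | dlPFC minus angular gyrus | Yes |
| Criticality | Rest before stimulation (9.1) | dlPFC minus angular gyrus | No |
| E/I balance | Rest before stimulation (9.1) | dlPFC minus angular gyrus | No |

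**4. Illustrative size.** Write A = k × D. The contrast is then D − kD = (1 − k)D. The protocol gives no k, so these values are assumed.

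- k = 0: 100% of D
- k = 0.5: 50% of D
- k = 1: 0% of D

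**5. What that would do to power (illustration only).** Section 9.2 states 80% power at d = 0.53 with 30 participants. For a paired t-test, two-sided at 0.05, df = 29, the noncentrality is d × √30.

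- k = 0: d = 0.53, noncentrality 0.53 × 5.477 = 2.90, power 80.1%. This reproduces the stated figure.
- k = 0.25: d = 0.3975, noncentrality 2.18, power 55.8%.
- k = 0.5: d = 0.265, noncentrality 1.45, power 28.9%.

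The d in Section 9.2 refers to 2-back performance. Applying it to an EEG marker is a further assumption, so these figures show direction only.

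**The case against.** **The comparator is not hidden.** The synopsis sentence itself says that cTBS goes to one site or the other, and Sections 4.1, 6.1.1 and 6.1.2 describe the active control fully and justify it. Section 9.4.2 nowhere says that the contrast is against no stimulation. This stands. The active-control crossover is coherent. The fault lies in the label and in what the 9.4.2 coefficient is taken to mean.

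**The first primary objective is not left without an analysis.** A reader might infer from the identical dosing that the trial can deliver only a site difference and so cannot address cTBS-induced sub-criticality at all. The protocol does not support that. Section 9.4.1 plans pre-post tests for E/I and criticality, Section 9.4.8 reports each participant's values before and after stimulation, and 9.1 uses rest before stimulation as the reference. If cTBS acted equally at both sites, the site contrast would be null and the pre-post tests could still show change. What remains is that 9.4.2 names the regression, not the pre-post test, as primary for these outcomes. Also, with no unstimulated session, pre-post change alone cannot be separated from time in session.

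**The loss of signal cannot be quantified.** A reader might infer that k must exceed zero, because Section 6.1.1 says cTBS lowers the E/I ratio at varied cortical sites. That does not follow for the modelled measure. Sections 3 and 9.1 predict local effects near the stimulated site. If the same channels near dlPFC are compared in both sessions, a local angular gyrus effect need not reach them and k could be near 0. If channels near each stimulated site are compared, k could be large. Section 9.4.2 does not say which channels enter the model.

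**Conclusion.** The contradiction is explicit and rests on the text alone. The synopsis and the primary analysis sentence claim a sham control that the design does not have and that Section 6.1.1 argues against. The trial is active-site-controlled.

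The 9.4.2 coefficient is therefore a difference between two sites under the same dosing rule. It fits the working memory and effort objectives. It does not test the 9.1 predictions on E/I and criticality, and a null for those outcomes cannot be read as absence of a cTBS effect.

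No sample size, alpha, stated power or dose is affected; what changes is the conclusion the primary model allows. The size of any attenuation, 1 − k, depends on an unknown k and is illustrative only.

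**What to change.** 1. In Section 1.1, replace *sham-controlled* with *active-site-controlled*, and *(sham)* with *(active control)*.
2. In Section 9.4.2, replace *target versus sham* with *dlPFC versus angular gyrus (active control)*. State that the coefficient is a site difference, and that a null for E/I or criticality will not be reported as absence of a cTBS effect.
3. Align 9.4.2 with 9.1: name the pre-post comparison already planned in 9.4.1 as the analysis for E/I and criticality, and report the site contrast as the test of site specificity. Note beside it that, without an unstimulated session, pre-post change cannot be separated from time in session.
4. Keep the first primary objective as it stands. Rewording it against angular gyrus stimulation would contradict 9.1, which sets criticality against rest before stimulation.

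The cost is a wording amendment, with no change to sample size, procedures or data collected. The downside is that the claim for the first primary objective then carries the stated time-in-session limitation.
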